EFFECTIVENESS ASSESSMENTS	Efficacy of Nighttime Aligners (worn 10-12 hours per day or night) will be assessed by demonstrating no statistically significant difference between expressed tooth movement versus programmed tooth movement at the end of treatment when compared to the Daytime aligners (worn 20-22 hours day/night). Quantification and comparison of expressed and programmed tooth movements will be conducted using Peer Assessment Rating (PAR) index to measure orthodontic treatment need and outcome, using the built-in weighted PAR analysis tool of 3Shape Ortho System software.
SAFETY ASSESSMENTS	The primary safety endpoint of the study will be the incidence of (device or dental) related AEs associated with the planned investigational treatment, as well as the occurrence of SAEs. Additionally, safety will be assessed through a post-treatment questionnaire administered to the subject asking about subject perceived comfort during treatment. Results will be quantified using a visual analogue scale. Both numerical values and a Wong Baker face scale will be used.
INCLUSION CRITERIA	
 
For inclusion in this clinical study subjects must meet all of the following criteria: 
 
Subject willing to participate in the clinical study and able to understand the content of the clinical study.
 
 
 
Subject must have permanent dentition (i.e. all second molars).
 
Subject must be 12 years of age or older.
 
Subject must be able to provide and sign consent for themselves, without requiring consent to be given by a legally authorized representative. Parental consent is also required for all participants who are not of the legal age to provide consent themselves (based on participant state of residence).
 
The subject requires correction of teeth without planned extrusive movements on either or both arches.
 

	
 
The subject has no greater than 5 mm of crowding and/or spacing (based on estimation by Investigator).
 

	
 
The subject does not require planned correction of molar tooth positions, posterior bite or molar classic relationship corrections. Subjects with Class II or Class III malocclusions requiring posterior bite / class correction are not eligible.
 

	
 
Subjects without prior orthodontic treatment within the past 18 months.
 

	9. Subjects who are periodontally stable.
	10. Subjects without a known history of plastic allergies.

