#### 9. ENDPOINTS

# 9.1 **Primary Safety Endpoint**

The primary safety endpoint of the study will be the incidence of (device or dental) related AEs and SAEs associated with the planned investigational treatment, compared to the incidence from treatment with the control device.

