# 11. ADVERSE EVENTS AND SERIOUS ADVERSE EVENTS

#### 11.1 Adverse Event (AEs)

- 11.1.1 All adverse events must be reported to the divisional complaint officer and regulatory compliance.
- 11.1.2 All Adverse Events (AEs) will be documented and recorded by the Investigator in the eCRF throughout the study period.
  - AE is defined as: Any untoward medical occurrence, unintended disease, effect or injury, or untoward clinical sign in a subject, whether related to the investigational product or not.
  - For example, a rash, bleeding, or blistering appearing on the soft tissue in contact with the investigational device.
  - Another example is clinically significant root resorption.
- 11.1.3 All adverse events shall be reported for that particular study subject's

appointment.

- This documentation should list the event, the cause of the event if known, consequences and resulting actions by the Investigator, or designee, and any other medically pertinent information.
- Where possible, a diagnosis rather than a list of symptoms should be given.
- The intensity to be recorded is the worst intensity experienced during the course of the event. The Investigator should complete all related information, including date(s) of onset, severity, corrective therapies given, outcome, and professional opinion as to whether the AE had a relationship to the investigational device.
- 11.1.4 The Center of Clinical Research (CoCR) team must make the determination of relationship to the investigational device for each recorded AE in the corresponding **eCRF**. The CoCR should decide whether there is a reasonable possibility that the event may have been caused by the investigational device.
- 11.1.5 If there is any valid reason, even if undetermined or untested, for suspecting a possible cause-and-effect relationship between the investigational device and the occurrence of the AE, then the AE should be considered "possibly" or "probably related".
- 11.1.6 Otherwise, if no valid reason exists for suggesting a relationship, then the AE should be classified as "unrelated". The following guidance may also be helpful:
  - Unrelated: There is no medical evidence to suggest that the AE is related to the investigational device. The AE can be readily explained by the subject's underlying medical condition or concomitant therapy or lacks a plausible temporal relationship to investigational device.

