#### 12.2 Data Analysis

- 12.2.1 The Sponsor and Investigators are not blinded to the study data during the conduct of the trial, and may at periodic intervals analyze the data to assess study progress.
- 12.2.2 If nothing else is stated, descriptive statistics will be given for each variable in the clinical study and p-values may be complemented by confidence intervals as appropriate. When using the terminology descriptive statistics, it is meant that the number of subjects (N), mean, median, standard deviation (Sd), minimum (Min) and maximum (Max) values will be presented for continuous data and frequencies and percentages for categorical data.

- 12.2.3 All tooth movement data analyses will be performed using 3Shape Ortho System (K152086).
- 12.2.4 Three .stl files from each subject would be used for the analysis:
  - A pre-treatment STL file (TS) would be generated by scanning subject's pre-treatment intraoral scan taken before the start of treatment.
  - A planned or programmed STL (TP) file would be obtained from Archform Orthodontic Software System (K213916) after planned or programmed tooth movements have been made based on the treatment plan finalized by the digital lab and study Investigators.
  - The actual post-treatment STL file (TF) would be generated by scanning subject's post-treatment intraoral scan at the end of treatment.
- 12.2.5 Each STL file would convert into a Digital Study Model within the 3Shape Ortho System software to standardize the analysis.
- 12.2.6 Each DSM would be segmented using the "auto segmentation tool" of the software to demarcate each tooth separately.
- 12.2.7 This would be followed by Peer Assessment Rating (PAR) index to measure orthodontic treatment need and outcome (Richmond, 1992). This would be done using the built-in weighted PAR analysis tool of 3Shape Ortho System software. The PAR index will be performed by an external evaluator.
- 12.2.8 The weightage for each component of the PAR index would be set as: maxillary and mandibular anterior segment alignment x 1; buccal occlusion x 1; overjet x 6; overbite x 2; centerline x 4; following the ABO guidelines. The weighted PAR scores for each DSM would be compared as follows:

The PAR Score values for  $T_S$ ,  $T_P$ , and  $T_F$  will be transferred to the eCRF and the following will be calculated:

- Planned percentage reduction in PAR Score (Planned Improvement of Malocclusion [PIM]) = PAR Score TS- PAR Score TP / PAR Score TS \* 100

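### The primary safety endpoint depends on a relatedness call made by CoCR, with no rule for how the investigator's opinion enters or how control-arm events are classified

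*Combined protocol and SAP*

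**What the plan says.** **Endpoint.** Section 9.1 states: "The primary safety endpoint of the study will be the incidence of (device or dental) related AEs and SAEs associated with the planned investigational treatment", to be compared with the incidence under the control device. Section 12.3.2 repeats that safety is evaluated on related AEs and SAEs, without naming whose assessment defines related. The Protocol Synopsis words the SAE part differently, adding "as well as the occurrence of SAEs" to the related AEs.

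**Two causality assessments.** Under 11.1.3 the investigator completes the event record, including a "professional opinion as to whether the AE had a relationship to the investigational device". Under 11.1.4, "The Center of Clinical Research (CoCR) team must make the determination of relationship to the investigational device for each recorded AE", and further, "The CoCR should decide whether there is a reasonable possibility that the event may have been caused by the investigational device".

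**Threshold.** Section 11.1.5 sets a low bar: "If there is any valid reason, even if undetermined or untested, for suspecting a possible cause-and-effect relationship", the event is to be rated possibly or probably related. Under 11.1.6, unrelated is reserved for events with no valid reason to suspect a link. The scale in 11.1.4 to 11.1.6 names only the investigational device.

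**Masking and oversight.** Section 12.2.1 says: "The Sponsor and Investigators are not blinded to the study data". Section 12.3.1 plans no Data Safety Monitoring Board. PAR scoring goes to an external evaluator (12.2.7), but no masked or external assessment of AEs is described.

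**CoCR's other tasks.** It verifies CRFs against source (13.3.2, 13.4.1), declares data clean and locks them (13.2.2), assists in the statistical analyses (14.1.2), and may view all relevant source documents (15.1.3).

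**The concern.** For non-serious AEs, the relatedness call is a filter between what happens to subjects and what the endpoint counts. If the person applying the filter knows which aligner was worn, different strictness in the two arms changes the comparison even when the underlying events do not differ. It can equally hide a difference that exists. An analyst who receives events already classified cannot detect this from the related-AE counts.

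Non-serious events matter here. Section 11.1.9 lists mild to moderate gum pain, inflammation and redness among the known events of orthodontic treatment. For such events, whether the aligner was the cause is a matter of judgement. Section 7.1.1 itself names greater discomfort as a risk that may increase with reduced wear time.

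The silence on disagreement is a second problem. If the rule is chosen after unblinded data have been reviewed, which 12.2.1 permits, the choice itself becomes open to challenge in a study meant to support FDA clearance (2.1.3).

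**Working it through.** **1. The plan's own figures.** No figure in the plan bears on this point. The only computed design figure is 23 per arm (12.1.2: SD 1, difference 1, power 0.90, two-sided alpha 0.05). It reproduces: 2 × (1.960 + 1.282)² × (1/1)² = 21.0, so 22 by the normal formula. The t-test solution is 22.02, so 23, with power 0.912. It concerns efficacy only and says nothing about AE rates.

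**2. The sections side by side.**

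| Question | What the plan gives |
|---|---|
| Who records a causality opinion? | Investigator (11.1.3) |
| Who makes the determination? | CoCR (11.1.4) |
| Which of the two defines related in the analysis? | Not stated in 9.1 or 12.3.2; 11.1.4 points to CoCR |
| What happens if they disagree? | Not stated |
| Which device does the scale cover? | Investigational device only (11.1.4 to 11.1.6), although 9.1 compares with control |
| Who judges dental relatedness? | Not stated |
| Is CoCR masked to arm? | Not stated; its source-data, lock and statistics roles make knowledge of the arm likely |
| Who can enter a CoCR rating? | Unclear: 11.1.4 can be read as CoCR recording it in the eCRF, while 13.4.2 lets only site staff modify eCRF data |

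**3. Illustration of the mechanism (all rates assumed).** The documents give no AE rates, so these numbers show how the filter works and are not a forecast.

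*No true difference.* Suppose 10 of 50 subjects per arm have an event that the investigator calls related: 10/50 = 20% in each arm. If 3 test-arm cases are downgraded, the test arm shows 7/50 = 14% against 20%. Fisher's exact test on 7/50 versus 10/50 gives p = 0.60, so the shift would not create a significant result.

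*A true difference.* Suppose 20% control and 40% test, with a share s of related test-arm cases downgraded. The observed test rate is 0.40 × (1 − s). The plan names no test for this endpoint. I used the normal approximation for two proportions, two-sided 5%, with n subjects per arm:

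power = Φ{[|pT − pC|√n − 1.96√(2p̄(1 − p̄))] / √(pT(1 − pT) + pC(1 − pC))}

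For s = 0 and n = 50: (1.414 − 1.270)/0.632 = 0.228, so power is 0.59.

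| s | Observed test rate | Observed difference | Power, n = 50 | Power, n = 23 |
|---|---|---|---|---|
| 0 | 40% | 20 points | 0.59 | 0.31 |
| 10% | 36% | 16 points | 0.43 | 0.22 |
| 20% | 32% | 12 points | 0.28 | 0.15 |
| 30% | 28% | 8 points | 0.15 | 0.09 |

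Starting from 10% versus 30%, a 30% downgrade leaves 11 points; from 30% versus 50%, it leaves 5 points. The comparison is weak even without downgrading, and one-sided downgrading mainly makes a real excess harder to see.

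**The case against.** A reader might take more from these sections than they support. Four stronger readings are tempting.

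- **That the investigator's opinion does not count.** The documents do not say so. It is a fair inference from the contrast between an opinion in 11.1.3 and a determination in 11.1.4, but what is documented is the absence of a rule.
- **That CoCR is unblinded by design.** Section 12.2.1 names the sponsor and investigators. CoCR's knowledge of the arm is inferred from its tasks.
- **That only related events enter the endpoint.** On the synopsis wording, SAEs may count whatever their cause, and 11.2.2 leaves part of the SAE classification to the investigator. The exposure is clearest for non-serious AEs.
- **That a downgrade would leave no trace.** All AEs are recorded whether related or not (11.1.2), eCRF changes are audit-trailed (13.4.5), and the general rule of descriptive statistics for each variable (12.2.2) could be read to cover all AEs. The trace is missing only from the related-AE comparison.

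The best defence is the threshold in 11.1.5 and 11.1.6: a dentist's reasoned suspicion is hard to dismiss as no valid reason. That stands as a real limit on downgrading. CoCR still decides what counts as a valid reason, however, and the threshold does not settle a disagreement. The independent contractor in 12.2.11 does not help, because classification happens before the analysis.

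It is also fair to say that an either-assessor rule does not remove bias: investigators are unblinded too and could over-call in one arm. That objection stands, and it is why the rule needs an all-causality comparison beside it.

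**Conclusion.** The concern holds in limited form. The primary safety comparison rests on related AEs. The plan assigns the relatedness determination to one team that probably knows the arm, collects a second opinion without giving it a role, and words the scale for one device when two must be classified. These are gaps in specification, visible in the text.

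No bias is shown, and its size cannot be estimated from the documents. The figures above rest on assumed rates and on downgrading in one arm only. The conclusion that CoCR probably knows the arm rests on its listed tasks. No safety margin or named test is given for this endpoint, so no planned conclusion can be shown to change. This is a change worth making because it is cheap and removes dependence on a single judgement; it does not make the study unsound.

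**What to change.** 1. State in 9.1 and 12.3 that an AE counts as related if either the investigator or CoCR rates it possibly related, probably related or related to the aligner worn, test or control. Reword the scale in 11.1.4 to 11.1.6 to match.
2. Add to 12.3 a comparison by arm of all AEs regardless of causality, shown beside the related AEs. No causality judgement can alter this table, although the decision to record an event remains unmasked.
3. List by arm every event on which the two assessors disagree.
4. Name who judges dental relatedness, and reconcile 11.1.4 with 13.4.2 on who enters the CoCR rating.

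Settle this before data accrue. The cost is wording in a few sections, one extra table and one listing. The related-AE rate may come out somewhat higher. The eCRF is not among the documents, so it must be confirmed that it holds the two assessments separately; if it does not, a field has to be added.

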# 1. STUDY OBJECTIVES

# 1.1 **Primary Objective:**

The primary efficacy objective of this study is the comparison between groups of the quantification of actual vs planned tooth movements. Changes in tooth position from pre-treatment baseline to end of treatment results will be measured for both Daytime Aligners (control) and Nighttime Aligners (test).

The safety objective of the study will be the incidence of (device or dental) related AEs associated with the planned investigational treatment, in comparison to the incidence of AEs associated with control treatment.

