  - Possibly Related: A direct cause and effect relationship between the investigational device and the AE has not been demonstrated, but there is a reasonable possibility that the AE was caused by the investigational device.
  - Probably Related: The AE is likely related to the investigational device. This category applies when the experience most likely seems to be related to the investigational device but there is a modest suspicion that it could be related to other causes.
  - Related: There is a direct cause and effect relationship between the AE and the investigational device.
- 11.1.7 The medical assessment of related AE severity will be determined by

using the following definitions:

- Mild: The AE is easily tolerated and does not interfere with usual activity.
- Moderate: The AE interferes with daily activity, but the subject is still able to function.
- Severe: The AE is incapacitating, and the subject is unable to work or complete usual activity, i.e. a serious injury has occurred.
- Life Threatening: The SAE places the subject, in the view of the Investigator, at immediate risk of death from the reaction as it occurred, i.e., it does not include a reaction that had it occurred in a more severe form, might have caused death.
- 11.1.8 Outcome may be classified as resolved, ongoing, resolved with sequelae, or death.
  - Unexpected severe or life threatening related events will be followed until resolved (the subject's health has returned to his/her baseline status or all variables have returned to normal), an outcome is reached, stabilization (the Investigator does not expect any further improvement or worsening of the AE), or the event is otherwise explained regardless of whether the subject is still participating in the study.
  - Where appropriate, medical testing and examinations will be performed to document AE resolution.
- 11.1.9 The types of adverse events that are known to occur with orthodontic treatment include mild to moderate gum pain, inflammation, and redness; allergic reaction to plastic(s) or metal(s); and root resorption.

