# 11.3 Device Deficiencies (DDs)

- 11.3.1 Device Deficiency (DD) is defined as: Inadequacy of a medical device with respect to its identity, quality, durability, reliability, usability, safety, or performance.
  - Device deficiencies include malfunctions, use errors, and inadequacy in the information supplied by the manufacturer including labelling.
  - This definition includes device deficiencies related to the investigational medical device or the comparator.
- 11.3.2 All DDs must be reported to the divisional complaint officer and regulatory compliance.

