# 12.3 Safety Analysis

- 12.3.1 As this is a non-significant risk study, the Sponsor does not intend to use a Data Safety Monitoring Board for this clinical study.
- 12.3.2 Safety aspects of the investigational device will be evaluated in terms of related adverse events (AEs) and serious adverse events (SAEs) documented during the course of treatment beginning at the time of application of the device through the time of completion of the treatment period; i.e., the time of removal of the final treatment aligner.
- 12.3.3 Evaluation of adverse events will be based on the risk management file and known risks/harms documented by Sponsor for aligner systems (e.g. design / process FMEAs, harms libraries, historical complaint files and post-market surveillance data).

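### The causality wording for adverse events names only the investigational device and does not expressly cover the control aligner, although the primary safety endpoint compares related events between arms

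*Combined protocol and SAP*

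**What the plan says.** **Endpoint.** Section 9.1 defines the primary safety endpoint as the incidence of device- or dental-related AEs and SAEs on the investigational treatment, "compared to the incidence from treatment with the control device". The safety objective in 1.1 is also comparative: "in comparison to the incidence of AEs associated with control treatment".

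**Causality rules.** Section 11.1.3 asks the investigator for a "professional opinion as to whether the AE had a relationship to the investigational device". Section 11.1.4 gives the determination for each recorded AE to the Center of Clinical Research (CoCR): "The CoCR should decide whether there is a reasonable possibility that the event may have been caused by the investigational device". Section 11.1.5 and the four categories in 11.1.6 use the same reference device. The top category, for example, reads: "There is a direct cause and effect relationship between the AE and the investigational device".

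**Safety analysis.** Section 12.3.2 begins: "Safety aspects of the investigational device will be evaluated in terms of related adverse events (AEs) and serious adverse events (SAEs". It does not mention the control device.

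**Device deficiencies, by contrast.** Section 11.3.1 does cover both arms: "This definition includes device deficiencies related to the investigational medical device or the comparator". Section 11.1 has no matching sentence.

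**The concern.** Relatedness decides which events enter the numerator of the primary safety endpoint, so it has to be judged by the same rule in both arms. Section 6.1 labels the Nighttime aligner investigational and the Daytime aligner control. A control subject does not wear the Nighttime aligner. If the assessor follows the wording, an AE caused by the Daytime aligner has no link to the investigational device and goes to the unrelated category.

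Section 9.1 also counts dental-related events, and 11.1 gives no rule for judging that limb in either arm.

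At stake is the comparison of related AEs with the cleared aligner, in a study meant to support substantial equivalence. Under literal coding the error runs against the sponsor's own test device. If some control events are judged against the aligner actually worn and others are not, the control incidence falls somewhere between zero and its true value, and the report would not show where.

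**Working it through.** **Step 1. Which device each provision names.**

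| Provision | Device named | Control aligner expressly covered? |
|---|---|---|
| 9.1 primary safety endpoint | test and control | yes |
| 1.1 safety objective | test and control | yes |
| 11.1.3 investigator's causality opinion | investigational | no |
| 11.1.3 record of the event's cause, if known | none specified | not excluded |
| 11.1.4 CoCR determination | investigational | no |
| 11.1.5 rule for suspected causes | investigational | no |
| 11.1.6 four categories | investigational | no |
| 11.3.1 device deficiencies | investigational or comparator | yes |
| 12.3.2 safety analysis | investigational | no |

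The endpoint needs a related count in both arms. The rules that produce the count name one arm's device.

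**Step 2. What literal coding does.** Let p_T and p_C be the true proportions of subjects with an aligner-caused AE, and let s be the share of such control subjects whose event is judged against the aligner they actually wear. If test-arm events are coded correctly:

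observed difference = p_T − s × p_C

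Literal coding is s = 0. Coding against the assigned aligner is s = 1. With p_T = p_C = p, the spurious difference is p × (1 − s).

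**Step 3. Illustration.** The documents give no AE rates and no figure for the safety comparison, so there is nothing of the plan's own to reproduce here. The 23 per arm in 12.1.2 is the efficacy sample size. Assume p = 20% and use the planned enrolment of 50 per arm (4.2), which gives 10 true events per arm:

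- s = 0: 10/50 versus 0/50, a difference of 20 points (Fisher's exact p = 0.001)
- s = 0.5: 10/50 versus 5/50, a difference of 10 points (p = 0.26)
- s = 1: 10/50 versus 10/50, a difference of 0

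**Step 4. Chance of a false significant excess on the test device if s = 0.** Against a control count of zero, two-sided Fisher p < 0.05 needs at least 5 events of 23 (p = 0.049) or 6 of 50 (p = 0.027). The chance is the binomial upper tail P(X ≥ 5 | 23, p) or P(X ≥ 6 | 50, p):

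| Assumed true rate, both arms | 23 per arm | 50 per arm |
|---|---|---|
| 10% | 7% | 38% |
| 20% | 50% | 95% |
| 30% | 86% | 99.9% |

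With the same rule in both arms, the chance of a significant difference in either direction over these rates is 1.6% to 2.5% (23 per arm) and 1.8% to 3.1% (50 per arm). The protocol names no test for safety; Fisher's test is my choice. These figures show how the mechanism works. They do not forecast what will happen.

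**The case against.** The strongest reply is that the protocol's use of the term is mixed, so the control aligner is not plainly shut out. The abbreviation list equates investigational product with investigational device, yet section 6.2, headed with that product term, opens by requiring that control devices be accounted for too. Section 6 is headed for the investigational device and describes both aligners. Section 11.1.4 requires a determination for each recorded AE, control subjects included, and an assessor who knows 9.1 would probably ask about the aligner worn. One team, the CoCR, makes the determination, so readings that vary from site to site are less likely than if each site decided. A control arm with no related AEs would also be conspicuous to an unblinded sponsor, and the CoCR can raise queries and unlock the eCRF.

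Much of this stands. It makes the wording ambiguous rather than an unequivocal exclusion. But other sections name both devices when both are meant (6.2.1, 8.7.1, 8.9.3), and 11.3.1 adds the comparator where 11.1 does not. No sentence extends the AE scale to the Daytime aligner.

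A reader might go further and infer that control AEs cannot be classed as related at all, or that the safety comparison has no valid control data. The documents do not support that. All AEs are recorded in both arms whatever their relationship (11.1.2), SAEs likewise (11.2.3), and 11.1.3 asks for the cause where known without limiting it to one device. The synopsis counts the occurrence of SAEs. All-cause incidence therefore stays comparable, and control relatedness could be re-adjudicated, although doing so afterwards and unblinded is weaker than a rule set in advance.

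Nor is dental relatedness wholly without a basis. Section 11.1.9 lists events known to occur with orthodontic treatment, and 12.3.3 refers to known harms of aligner systems generally. Neither is a causality rule. The eCRF fields are not in the documents, so a suitable item may already exist.

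**Conclusion.** The point holds for the related-AE comparison in 9.1. The causality wording in 11.1.3 to 11.1.6 and the analysis statement in 12.3.2 do not expressly cover the control aligner. Read literally, they would code control-aligner AEs as unrelated, understate the control incidence and bias the comparison against the test device. Under mixed readings the amount of bias is unknown.

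The size cannot be established from the documents. The 20-point and 10-point gaps and the false-significance rates rest on assumed equal AE rates, correct coding in the test arm and, for the significance rates, fully literal coding of control events and a test the protocol does not specify.

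Severity: should fix. The rule as written can give a wrong result on a primary endpoint, but it concerns one component, the underlying data are collected in both arms, and the error can be recovered.

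**What to change.** 1. In 11.1.3 to 11.1.6, replace the reference to the investigational device with: the study aligner the subject is assigned (investigational or control).
2. In 12.3.2, refer to the investigational and control devices, and state that related AEs are reported by arm, in line with 9.1.
3. State how dental-related in 9.1 is judged, with the same rule in both arms. One additional eCRF causality item using the existing four categories would do; it is one option among several.

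The cost is a protocol wording change and at most one extra eCRF item. No visits, staff or subjects are added. If any AEs have been coded before the change, the CoCR should re-assess control-arm relatedness under the revised wording and document that it did so.
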